4.5 Termination of the Clinical Study

The sponsor has the right to terminate this study at any time. Reasons for terminating the study may include, but are not limited to, the following:

- The incidence or severity of adverse events (AEs) in this or other studies indicates a potential health hazard to subjects. Specifically, the study will be stopped if five or more patients report dehydration requiring hospitalization or allergic reaction requiring hospitalization
- Patient enrollment is unsatisfactory
- Upon request of health or regulatory authorities

The sponsor will notify the investigator if the study is placed on hold or if the sponsor decides to discontinue the study. Health authorities, regulatory authorities, and Independent Ethics Committees (IECs)/Institutional Review Boards (IRBs) will be informed about the termination of the study in accordance with applicable regulations.

5. INVESTIGATIONAL MEDICINAL PRODUCT

5.1. Identity of the Investigational Medicinal Products

Study treatments include a pharmaceutical form of the active substance being tested, aldafermin, and a matched placebo being used as a reference.

5.2. Drug Accountability, Dispensing, and Destruction

The study pharmacist will maintain accurate records of receipt of all study treatment materials. In addition, accurate records will be kept regarding when and how much study treatment is dispensed and used by each subject. Reasons for deviation from the expected dispensing regimen also must be recorded. Study treatment will be reconciled. The study pharmacist will provide access to study treatment and study treatment records as required for reconciliation to be timely completed.

At the conclusion of the study, any used and unused study treatment containers will be returned to the sponsor or designee, or destroyed, after data review is complete, as per sponsor instructions. If no supplies remain, this fact will be documented in pharmacy product accountability records.

5.3. Administration of Investigational Medicinal Products

Unblinded pharmacy personnel will be responsible for providing aldafermin or placebo to blinded study personnel for dispensing as per the randomization scheme. Study treatment will be dispensed to subjects in a

blinded manner.

Patients will self-administered study treatment by subcutaneous injection into the abdomen once daily at approximately the same clock time each day during the treatment period. Patients will be counseled on the importance of administering study treatment as instructed and of recording the time of each dose accurately in the patient's bowel pattern diary throughout the treatment period.

5.4. Compliance

As this is a multiple-dose study, treatment compliance will be assessed for each administration of study treatment. Comments will be recorded if there are any deviations from planned study treatment administration procedures.

5.5. Randomization

Patients who complete screening assessments and meet all eligibility criteria will be assigned a unique randomization identification number at the time of study treatment administration. Once a randomization number has been allocated to a subject, it may not be assigned to another patient.

DESIGN: Randomized placebo-control trial based using **BLOCK RANDOMIZATION** so that equal numbers of patients are randomized to placebo and aldafermin 1 mg in two blocks:

- a. Patients OFF bile acid sequestrants**
- b. Patients ON bile acid sequestrants.**

Randomized treatment assignment will be considered blinded as per the following: The randomization assignments will be available to the study pharmacy staff that is preparing the study treatment, who will not be involved in any other aspect of the study including administration of the study treatment. Randomization assignments will not be made available to the patients or study staff responsible for the monitoring and evaluation of safety assessments.

In the absence of a medical emergency, the blinded randomization for this study will not be revealed to the Principal Investigator and study team until all data are entered in the database, edit checks are performed, queries closed, and the database is officially locked.

Breaking the blind is expressly forbidden except in the event of a medical emergency where the identity of the study treatment must be known in order to properly treat the patient. In the event of a medical emergency, it is requested that the investigator contact the sponsor prior to breaking the blind. If breaking the blind is required because of a medical emergency, the treatment identity would be revealed by the investigator or designee, for that patient only. Reasons for treatment unblinding must be clearly explained and documented.

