Statistical Methods	
Sample size: 30 patients, 15 in placebo group, 15 in aldafermin treatment group.
 
Statistical analyses: Effects of treatment will be compared using Intent-to-Treat principles using ANCOVA with BMI, gender and baseline fasting C4 as covariates. Adverse events (AEs) will be listed and summarized by system organ class and preferred term, as well as according to severity and causality/relationship to study treatment. Observed values for clinical laboratory tests, vital signs and safety 12-lead ECGs will be summarized by treatment. Observed values will be classified as normal, abnormality that is not clinically significant, and clinically significant abnormality by treatment. Results of other safety assessments will be listed and summarized as appropriate.
 
Statistical power: Based on the prior open-label study, the proposed sample size of 15 per group has ~80% power (2-sided $\alpha=0.05$) to detect clinically relevant effect sizes in serum C4 and stool consistency.
 
Anticipated results and significance: Aldafermin will reduce serum C4 and percent

[figure not shown]
	fecal primary bile acids in a random stool sample; preliminary data will be obtained regarding efficacy on stool frequency and stool consistency in BAM/BAD with high BA excretion.
--	---

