3. STUDY DESIGN

3.1 Overview

This single-center, randomized, double-blind, placebo-controlled study is designed to evaluate the effects of aldafermin on daily bowel pattern, fasting serum C4 and FGF-19 and fecal bile acid excretion in a random stool sample in patients with BAM/BAD. The study includes a screening period (up to 28 days) and two 14-day treatment periods for a maximum duration of up to 56 days. Eligible patients will be randomized into 2 blocks, those staying of bile acid sequestrants and those not taking them, and stratified by gender and BMI, we anticipate 90% female and 75% $BMI > 30 \text{ kg/m}^2$. A schematic diagram of the study design is shown below.

Aldafermin Study Design

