7. STATISTICAL CONSIDERATIONS

7.1 Sample Size and Statistical Power

Based on the endpoints of interest in patients with bile acid diarrhea [12], the proposed sample sizes have ~80% power (2-sided $\alpha=0.05$) to detect clinically relevant effect sizes in serum C4 and stool form (expressed as detectable difference $[\Delta]$ in 2 groups:

Table 1: Detectable differences based on 80% power in patients with BAD *not* receiving BA sequestrant

Response	Mean (SD)	Detectable Δ absolute with n=9 per group
Serum C4 ng/mL	72.3 (45.6)	64.1 (1.34*SD or 89 % of baseline mean)
% fecal primary BA	15.7 (20)	28.1 (1.79*SD or 179 % of baseline mean)
# BMs per week	15.1 (7.1)	10.0 (1.41*SD or 66 % of baseline mean)
Stool form (BSFS 1-7 scale)	4.4 (1.12)	1.58 (1.41*SD or 35.9 % of baseline mean)

Based on our previous open-label study demonstrating effects of a bile acid sequestrant (colesevelam) as a typical baseline results for patients on bile acid sequestrants:

Table 2: Detectable differences based on 80% power in patients with BAD receiving BA sequestrant

Response	Mean (SD)	Detectable Δ absolute with n=6 per group
Serum C4 ng/mL	112.5 (50.6)	90.8 (1.79*SD or 80.7 % of baseline mean)
% fecal primary BA	2.7 (7.4)	13.3 (1.80*SD or 492% of baseline mean)
# BMs per week	21.7 (7.1)	12.75 (1.80*SD or 58.8 % of baseline mean)
Stool form (BSFS 1-7 scale)	4.6 (0.6)	1.08 (1.80*SD or 23.5% of baseline mean)

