7.2 Statistical Analysis

Effects of treatment will be compared using Intent-to-Treat principles using ANCOVA with BMI, gender and baseline fasting C4 as covariates. In order to reach 30 subjects, accrual will be set at 36 to replace any volunteer(s) who withdraw prior to taking less than 1 day of dosing. Any Subject who receives more than 1

day of dosing will be consider completed using the Intent-to-Treat analysis.

Primary endpoints are change in fasting serum C4 levels from baseline to Day 28 and change in stool consistency based on Bristol Stool Form Scale, BSFS from baseline to Day 28.

Secondary endpoints are

- Absolute change in stool consistency from baseline to Day 14 and Day 28 of treatment
- Average daily stool consistency score at Day 14 and Day 28 of treatment
- Maximum abdominal pain score rated by patient using an 11-point scale, 0 to 10 inclusive with 0 as none and 10 as worst imaginable pain
- Absolute change in abdominal pain from baseline to Day 14 and Day 28 of treatment
- Number of bowel movements per week
- Change in total fecal bile acid concentration between baseline and Day 28
- Proportion of fecal secretory (CDCA+ DCA) bile acid as measured in a single, random stool sample by a validated laboratory assay.
- Proportion of fecal primary (CDCA + CA) bile acid as measured in a single, random stool sample by a validated laboratory assay.
- Total fecal bile acid concentration in a single, random stool sample as measured by a validated laboratory assay.
- Total aldafermin concentration in serum as measured by a validated laboratory assay

Adverse events (AEs) will be listed and summarized by system organ class and preferred term, as well as according to severity and causality/relationship to study treatment.

Observed values for clinical laboratory tests, vital signs and safety 12-lead ECGs will be summarized by treatment. Observed values will be classified as normal, abnormality that is not clinically significant, and clinically significant abnormality by treatment.

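### The ANCOVA leaves out bile acid sequestrant use (ON/OFF), the one randomization factor that Sections 3.1 and 5.5 both name; adding it costs one degree of freedom and gains little

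*Combined protocol and SAP*

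**What the plan says.** - **Randomization, Section 5.5:** "equal numbers of patients are randomized to placebo and aldafermin 1 mg in two blocks". The two blocks are patients off and patients on bile acid sequestrants. Gender and BMI are not mentioned.
- **Randomization, Section 3.1:** patients are "randomized into 2 blocks, those staying of bile acid sequestrants and those not taking them, and stratified by gender and BMI". The blocks are the same, with two further factors.
- **Sample size, Section 7.1:** each stratum has its own table. Table 1 (not on sequestrant) gives detectable differences "absolute with n=9 per group". Table 2, titled "Detectable differences based on 80% power in patients with BAD receiving BA sequestrant", gives them "absolute with n=6 per group". Together these make 15 per group.
- **Analysis, Section 7.2:** "ANCOVA with BMI, gender and baseline fasting C4 as covariates". The synopsis agrees: "Intent-to-Treat principles using ANCOVA with BMI, gender and baseline fasting C4 as covariates". Neither place has a term for sequestrant use, a stratified analysis or a treatment-by-stratum term.

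**The concern.** When randomization is balanced within a factor, the analysis should normally carry that factor. Otherwise, outcome differences between the strata stay in the residual variance, although the design has already removed them from the treatment comparison. The standard error is then somewhat too large, and power can be lost. The plan itself expects the strata to differ: its tables put mean C4 at 72.3 ng/mL off and 112.5 ng/mL on sequestrants. Gender and BMI, the extra factors in Section 3.1, are already covariates, so sequestrant use is the only named randomization factor missing from the model. What is at stake is precision in a 30-patient trial, and settling before unblinding whether to adjust for sequestrant use.

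**Working it through.** **1. The plan's own figures.** The detectable difference is d × SD, where d gives 80% power in a two-sided 5% two-sample t-test with 2n - 2 degrees of freedom.

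- n = 9 per group, d = 1.407: C4 1.407 × 45.6 = 64.2 (printed 64.1); stool form 1.407 × 1.12 = 1.58 (printed 1.58).
- n = 6 per group, d = 1.796: C4 1.796 × 50.6 = 90.9 (printed 90.8); stool form 1.796 × 0.6 = 1.08 (printed 1.08).

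All eight tabulated differences give power of 0.799 to 0.802. The tables are therefore unadjusted comparisons within each stratum, and no analysis in Section 7.2 corresponds to them.

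**2. Bias.** Allocation is 1:1 within each stratum (9 of 18 off, 6 of 12 on), so treatment is uncorrelated with stratum by design. Leaving stratum out cannot shift the estimate systematically. In simulation under no effect, the mean estimate without the factor was -0.003 to 0.001 on the log C4 scale.

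**3. How far the strata differ (Tables 1 and 2, levels).**

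- C4: pooled SD = √[(17 × 45.6² + 11 × 50.6²)/28] = 47.6; gap (112.5 - 72.3)/47.6 = 0.84 SD.
- Stool form: pooled SD = √[(17 × 1.12² + 11 × 0.6²)/28] = 0.95; gap (4.6 - 4.4)/0.95 = 0.21 SD.
- On the log scale, lognormal distributions matching the tabulated C4 means and SDs differ by 0.52.

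These are levels. Both primary endpoints are changes to Day 28, and the documents give no ON/OFF gap in change, so its persistence has to be varied.

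**4. Power without and with the factor.** There were 20,000 simulated trials per scenario, with 18 patients off and 12 on sequestrants. The model was an ANCOVA of change on treatment, BMI, gender and baseline C4, with or without ON/OFF. The 90% female share is from Section 3.1. Assumed: BMI mean 33 and SD 6, a 40% C4 reduction, the baseline-to-Day-28 correlation r, and the share of the gap persisting.

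| C4 scale and gap persisting | r = 0 | r = 0.3 | r = 0.5 | r = 0.7 |
|---|---|---|---|---|
| Log, whole | 61.3 → 67.7% | 69.0 → 72.1% | 78.3 → 79.7% | 92.3 → 92.5% |
| Log, half | 66.4 → 67.5% | 72.2 → 71.9% | 80.3 → 79.9% | 92.3 → 92.1% |
| Log, none | 68.9 → 68.1% | 71.3 → 71.6% | 78.1 → 79.5% | 88.8 → 92.1% |
| Raw, whole | 58.9 → 64.7% | 65.4 → 68.4% | 73.7 → 75.2% | 88.7 → 89.0% |

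On the raw scale the change is -0.7 to +0.7 points with half the gap persisting and -0.5 to +4.1 with none. In the log, whole-gap row the confidence intervals are 8.2%, 4.2%, 2.4% and 0.9% narrower with the factor.

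The gain at r = 0.7 with no gap persisting has a different source: if the baseline gap has vanished by Day 28, adjusting for baseline C4 itself creates a difference between strata, which the ON/OFF term removes.

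**5. Stool consistency.** For an assumed difference of 1 BSFS point, with r from 0.3 to 0.7 and the correlation of change with baseline C4 at 0 or 0.3, adding the factor changes power by -0.9 to +0.6 points if the whole or half the gap persists, and by -0.6 to +1.5 points if none does.

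**6. Test size.** Null rejection is 3.4 to 5.2% without the factor and 4.4 to 5.2% with it. The simulation standard error near 5% is √(0.05 × 0.95/20,000) = 0.15 points, so 5.2% is not evidence of inflation.

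**7. Degrees of freedom.** The current model has five parameters (intercept, treatment, BMI, gender, baseline C4), so 30 - 5 = 25. With ON/OFF there are 24. The detectable difference at 15 per group moves from 1.064 to 1.066 SD.

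**The case against.** The strongest reply is that the model choice changes almost nothing. Baseline C4 is already a covariate and carries part of the ON/OFF gap; the tabulated stool-form gap is only 0.21 SD; in several scenarios the extra term loses up to about a point of power; and the 6-point gain needs a patient's baseline and Day 28 C4 to be uncorrelated, which is an edge case. All of that stands, and it sets the priority. It does not argue for leaving the term out, because the worst loss is about one point and the possible gain is larger.

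Baseline C4 is also not a full substitute for stratum. It helps least on endpoints that C4 does not track. Bowel movements per week, a secondary endpoint, differ by (21.7 - 15.1)/7.1 = 0.93 SD in the tables. If that gap persists and C4 within stratum is unrelated to frequency (both assumed), power for a difference of 7.5 per week rises from 69% to about 74% with the factor.

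A second reply is that Sections 3.1 and 5.5 do not contradict each other: Section 5.5 describes the two blocks without saying that nothing else is stratified, so Section 3.1 may simply be the fuller account. That is fair. A reader might infer that the difference leaves the right model unclear. It does not: gender and BMI are covariates already, so the recommended model is the same whichever section describes the list.

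**Conclusion.** The point holds as a low-priority improvement. The ANCOVA omits the one randomization factor that both design sections name. The consequence is no bias, no type I inflation and a possibly conservative test. Adding the factor changes C4 power by about -1 to +4 points in most scenarios, about +6 in the extreme one, and stool consistency power by about -1 to +1.5 points.

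The omission and the absence of bias follow from the text and the design. The sizes rest on assumed effects, correlations, distributions and gap persistence.

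A reader might infer a larger loss from a simpler calculation that treats C4 as unrelated to outcome and to stratum: power of 69% against 75% for a 1.06 SD effect at a 0.84 SD gap, or test size of 1.8% at a 1.5 SD gap. The documents do not support carrying this over to the primary endpoints. It removes the adjustment that baseline C4 provides for the C4 endpoint; the tabulated stool-form gap is 0.21 SD; and no tabulated gap reaches 1.5 SD. Nor is there ground for calling the planned analysis invalid.

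**What to change.** Add sequestrant stratum (ON/OFF, as randomized) as a fixed factor to every ANCOVA in Section 7.2 and the synopsis, keeping BMI, gender and baseline fasting C4. This costs one residual degree of freedom (25 to 24 with 30 patients) and needs no new data and no change in sample size.

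As an editorial change only, make Sections 3.1 and 5.5 list the same stratification factors, matching the randomization list actually used. If BMI is one of them, state its cut-point; the 30 kg/m² in Section 3.1 appears only as part of the expected patient mix. This takes one aligned sentence and leaves the recommended model unchanged.

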5.6. Prior and Concomitant Medications

Any medication (including over-the-counter or prescription medicines, vitamins, and/or herbs/supplements) or vaccines that a patient uses from 30 days prior to Visit 1 Screen throughout the study must be recorded along with reason for use, dose and frequency and dates of use.

5.7. Rescue Medication

Because the study includes placebo treatment and is approximately 56 days long, loperamide may be used as a rescue medication except within 48 hours of a stool collection. The maximum dose of loperamide allowed is 4 mg in a 24-hour period. The use of loperamide as a rescue medication must be recorded in the bowel pattern diary.

6. STUDY ASSESSMENTS AND PROCEDURES

6.1. Screening and Eligibility

Patient eligibility will be assessed based on protocol inclusion and exclusion criteria. All screening evaluations must be completed and reviewed to confirm potential patients meet all eligibility criteria.

Screening procedures must be completed within 28 days prior to initiation of study medication.

At the Visit 1 Screen or during the optional remote consent and eligibility review, potential patients will have a detailed verbal presentation of the nature, purpose, risks, and requirements of the study in addition to receiving detailed written information. Patients will have adequate opportunity to ask the appropriate person of the study team (ie, Principal Investigator or designee) about any aspect of the study. If a patient decides that he/she is willing to participate in the study, he/she will be asked to sign the informed consent form. The clinical personnel obtaining written consent from the patient will also sign the form to confirm consent has been obtained. Once signed, the original consent will be maintained for the study records and a signed copy given to the patient. A copy will be scanned into the patient's electronic medical record. The investigator will verify that informed consent has been obtained from each patient prior to the patient undergoing any study-related procedures.

Visit 1 Screen consists of:

- Complete medical history
- Physical examination, including height, weight, and vital signs (heart rate, blood pressure, temperature and respiration rate)
- Safety 12-lead ECG
- Clinical laboratory tests: The standard Comprehensive Metabolic Panel which includes calcium, creatinine, sodium, potassium, albumin, alkaline phosphatase, total bilirubin, carbon dioxide, chloride, glucose, total protein, BUN, AST, and ALT. Hematology includes a CBC with differential. A lipid panel including total cholesterol, HDL, LDL and triglycerides will be performed. Analysis of the urine will be completed by a standard urine dipstick method with microscopy.

- Urine human chorionic gonadotropin (hCG) pregnancy test (for females of childbearing potential)

6.2. Adverse Event

An AE is any untoward medical occurrence that does not necessarily have a causal relationship with the study treatment. An AE can therefore be any unfavorable and unintended sign, symptom or disease temporally associated with the use of a medicinal product, whether or not considered related to the medicinal product.

Adverse events can include, but are not limited to, any of the following:

- Unfavorable changes in general condition
- Subjective or objective signs/symptoms
- Concomitant disease or accidents
- Clinically relevant adverse changes in laboratory parameters over the course of the study
- Pre-existing conditions that worsen in severity, increase in frequency, or have new signs/symptoms

6.3 Serious Adverse Event

An AE should be classified as an SAE if it meets one of the following criteria:

Fatal:	The AE resulted in death.
Life-threatening:	The AE placed the subject at immediate risk of death. This classification does not apply to an AE that hypothetically might cause death if it were more severe.
Hospitalization:	The AE required or prolonged an existing inpatient hospitalization. Hospitalizations for elective medical or surgical procedures or treatments planned before the signing of informed consent in the study or routine check-ups are not SAEs by this definition.
Disabling/ incapacitating:	The AE resulted in a persistent or significant incapacity or substantial disruption of the subject's ability to conduct normal life functions.
Congenital anomaly or birth defect:	An adverse outcome in a child or fetus of a subject exposed to the study treatment before conception or during pregnancy.

Medically significant: The AE did not meet any of the above criteria but could have jeopardized the patient and might have required medical or surgical intervention to prevent one of the outcomes listed above or involves suspected transmission via a medicinal product of an infectious agent.

The Principal Investigator will promptly review all information relevant to the safety of the investigational drug and notify the FDA of any unexpected fatal or life-threatening suspected adverse reaction as soon as possible, but no later than 7 calendar days after receipt of the information. The Principal Investigator will also notify the FDA in an IND safety report of potential serious risks, as soon as possible, but in no case later than 15 calendar days after the Principal Investigator determines that the information qualifies for reporting.

Elective hospitalization and/or surgery for clearly preexisting conditions (i.e., a surgery that has been scheduled prior to the patient's entry into the study) will not be reported as an SAE. All other hospitalizations, including elective hospitalizations for any condition that was not preexisting, will be reported as an SAE.

Any SAE that is ongoing when the patient completes the study or discontinues the study will be followed by the Investigator until the event resolves, stabilizes, or returns to baseline status.

